7.8 SCREEN FAILURES

A screen failure subject is a consented subject that did not have the procedure either due to withdrawing consent or being withdrawn from the study by the Investigator due to not meeting eligibility requirements for treatment.

If a subject signs the ICF but is found ineligible for inclusion in the study prior to or during the procedure, the subject will not be advanced any further in this clinical investigation. The subject's signed ICF and completed inclusion/exclusion criteria will be retained by the Investigator, and the subject will be notified.

Screening data, including the reason for exclusion, will be collected but may not be complete in cases where the subject is determined to be a screen failure early in the screening process. A record of all screened subjects will be maintained in a Screening & Enrollment Log. The subject's exclusion from the study and reason for ineligibility will be documented on the Screening & Enrollment Log.

NOTE: If a subject does not meet the eligibility criteria during their Screening Visit, the subject may be re-evaluated for entry into the study at a later time if deemed appropriate by the Investigator. These subjects will require formal written Sponsor approval, and the subject will need to be re-consented, sign a new informed consent form, and undergo a full review of the inclusion/exclusion criteria by the Investigator.

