7.10 SUBJECT ENROLLMENT

The point of enrollment occurs when the Investigator delivers the local anesthetic. All enrolled subjects, including those found to be ineligible after consent, will be followed for the next 30 days in accordance with the Schedule of Assessments.

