7.11 TREATED SUBJECTS

A treated subject is an enrolled subject who has had the OsteoProbe measurement procedure completed and a BMSi measurement was recorded. All treated subjects, including those found to be ineligible after enrollment, will be followed for the next 30 days in accordance with the Schedule of Assessments.

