10.2 SUBJECT WITHDRAWALS

Subjects have the right to withdraw from the clinical investigation at any time and for any reason without prejudice to their future medical care by the investigation team or investigational site. The Investigator will ask reason for their withdrawal and will record all information regarding the subject discontinuation. Per Section 7.8, subjects who withdraw consent prior to treatment will be regarded as screen failures.

A Subject may be withdrawn from the clinical investigation for reasons including but not limited to the following:

- Subjects may choose to withdraw from the clinical investigation under the terms of the Declaration of Helsinki and their consent documentation without having to give a reason;
- Any adverse event which, in the opinion of the Investigator, is related to the treatment and will endanger the well-being of the subject if treatment is continued;
- Development of any intercurrent illness(es), infection or condition(s) that might interfere with the clinical investigation;
- Non-compliance with the clinical investigation procedures deemed by the Investigator to be sufficient to cause discontinuation;
- Any problem deemed by the Investigator to be sufficient to cause discontinuation.

Regardless of the reason for withdrawal, data available for the subject at the time of withdrawal, including the reason for withdrawal, will be documented in the subject's study records. The Investigator will treat all subjects discontinued from the investigation due to an adverse event until the event resolves. A subject that has been withdrawn from the study after treatment will not be replaced.

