18.3 STUDY POPULATIONS

18.3.1 Primary Analysis Set

All subjects with a time of procedure start recorded will be included in the Primary Analysis Set. The Primary Analysis Set will be utilized in testing of the primary safety endpoint.

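### Sections 7.8 and 10.2 close out or relabel a subject found ineligible, or withdrawing consent, between the local anesthetic and the BMSi, while 7.10 requires 30-day follow-up and 18.3.1 may already count the subject in the primary analysis

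*Combined protocol and SAP*

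**What the plan says.** Two groups of sections decide what happens to a subject whose participation is questioned around the measurement.

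- **Closing out.** Section 7.8 defines the label: "A screen failure subject is a consented subject that did not have the procedure either due to withdrawing consent or being withdrawn from the study", the second reason being ineligibility. It adds that if a consented subject is "found ineligible for inclusion in the study prior to or during the procedure, the subject will not be advanced any further". For such subjects it describes keeping the consent form, the eligibility record, whatever screening data exist and a log entry. Section 10.2 says that "subjects who withdraw consent prior to treatment will be regarded as screen failures", citing 7.8. Section 7.11 defines a treated subject as "an enrolled subject who has had the OsteoProbe measurement procedure completed and a BMSi measurement was recorded".
- **Keeping.** Section 7.10 states: "The point of enrollment occurs when the Investigator delivers the local anesthetic". It continues: "All enrolled subjects, including those found to be ineligible after consent, will be followed for the next 30 days". Section 14.3.1 starts adverse event collection at the same point. Section 18.3.1 states: "All subjects with a time of procedure start recorded will be included in the Primary Analysis Set". Section 8.1 times the procedure start from the Tip first reaching bone, which comes after the anesthetic.

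Section 8.1 also covers a measurement that cannot be completed for any reason: device use stops and the subject is treated per standard of care. It attaches no screen-failure label and does not mention follow-up.

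**The concern.** The close-out rules run past the point at which 7.10 has already enrolled the subject. Anyone found ineligible during the procedure has, by the order of events in 8.1, already received the anesthetic, so the words 'or during' in 7.8 can apply only to subjects whom 7.10 says must be followed. The protocol states no order of precedence, and 7.8 is the section a site would consult for an ineligible subject.

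Such subjects have had the anesthetic and perhaps an indentation. The risks listed in section 4.1 include soft tissue infection, bone infection and fracture, which may not be evident on the day. The 1-, 7- and 30-day contacts are how they would be found. A subject closed out under 7.8 but counted under 18.3.1 enters the primary analysis without an observed 30-day outcome, and 18.4 accepts the alternative only when there are no events.

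**Working it through.** **1. The sections side by side, by stage**

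| Stage | Found ineligible (7.8) | Withdraws consent (10.2 with 7.11) | 7.10 | 18.3.1 |
|---|---|---|---|---|
| Before anesthetic | Goes no further | Screen failure | Not enrolled | Not in set |
| After anesthetic, Tip not yet at bone | Goes no further | Screen failure | Enrolled, 30 days | Not in set |
| Tip has reached bone, no BMSi | Goes no further | Screen failure | Enrolled, 30 days | In set |
| BMSi recorded | Not a screen failure | Not a screen failure | Enrolled, 30 days | In set |

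The first and last rows are consistent. In the second row the sections disagree on follow-up. In the third they disagree on follow-up and on whether the subject is a screen failure or an analysed subject. In that row 10.2 also sits badly with 7.8, which it cites, because the 7.8 definition covers only subjects who did not have the procedure.

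**2. The plan's own figure**

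Inputs from 18.1 and 18.2: Jeffreys prior Beta(0.5, 0.5); 215 prior subjects with 0 events; 40 prospective subjects; performance goal .01; threshold .975. With h prior subjects, n prospective subjects and x events, the posterior is Beta(0.5 + x, 0.5 + h + n − x), and the decision uses P(p < .01).

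- h = 215, n = 40, x = 0: Beta(0.5, 255.5) gives .9765. This matches the plan.

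**3. One event**

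- h = 215, x = 1: Beta(1.5, 254.5) gives .8368, which fails.
- h = 270 (the anticipated total in Table 8): .9875 with no event and .8989 with one, which fails.

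**4. Loss of numbers alone**

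With h = 215, no events, and unobserved subjects simply left out:

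- n = 39: .9762
- n = 35: .9751, which passes
- n = 34: .9748, which fails

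So up to five unobserved subjects are tolerable on numbers alone.

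**5. What 18.5 would do with one unfollowed subject**

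Take 39 observed subjects with no events. The chance that the missing outcome is imputed as an event is the posterior mean. Section 18.5 can be read in two ways on which data supply that posterior:

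- Prior and trial data together: 0.5 / (0.5 + 254.5) = 0.5/255 = .0020. Averaged over imputations: .0020 × .8368 + .9980 × .9765 = .9762, a pass.
- Trial data only, with the Jeffreys prior: 0.5 / (0.5 + 39.5) = 0.5/40 = .0125. Averaged: .0125 × .8368 + .9875 × .9765 = .9747, just short of .975.

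On the first reading the goal is met even if that subject had a device-related SAE that nobody recorded. On the second, the missing follow-up alone costs the goal even if nothing happened. Averaging the posterior probability over imputations is my assumption; 18.5 does not state the combining rule. With h = 270 both readings pass.

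**The case against.** A reader might infer that any measurement stopped midway turns the subject into a screen failure. The documents do not support that. Section 7.8 gives two reasons only, withdrawn consent and ineligibility. Device failure, operator difficulty or no BMSi displayed falls under the 8.1 instruction for incomplete procedures, and the 7.10 follow-up duty continues. A subject who asks to stop because of pain has not thereby withdrawn consent to the study.

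Other points on the other side:

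- **Section 7.10 speaks to the case.** It names subjects found ineligible after consent, there is one site, and the sponsor trains it. A careful investigator may well follow 7.10. That lowers the likelihood of harm but leaves two incompatible instructions.
- **Withdrawal of consent.** In the 10.2 route follow-up is lost mainly because consent is gone, whatever the label. This stands. The remaining defect there is the label, and that the text does not separate stopping the measurement from refusing later contact.
- **Data are kept.** Section 10.2 requires available data to be documented, 10.4 includes data already collected, and 14.4 provides for treatment of adverse events. These limit the loss but cannot supply an outcome that arises after close-out.
- **Section 18.5 includes best- and worst-case scenarios.** A worst case with one missing subject counted as an event gives .8368, so the dependence would be visible, but only as a sensitivity analysis.
- **Fragility to one event comes from the zero-event rule**, not from this conflict. This also stands: .8368 shows what one missed event would cost, not how likely one is.
- **Exclusion 7 (soft tissue)** could come to light at this stage. If it keeps the Tip from bone, however, no start time is recorded and the subject is outside the primary set. Only the follow-up conflict then applies.

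**Conclusion.** The inconsistency is real in the current text and narrow. It covers subjects found ineligible, or withdrawing consent, after the anesthetic and before a BMSi is recorded. All of them are enrolled under 7.10, and those in whom the Tip has reached bone are also in the Primary Analysis Set.

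The documents give no rate for this group, and after x-ray, examination and history screening it is probably small. As an illustration only, if 1 to 4 of 40 subjects were closed out and their device-related SAE rate equalled the 1% goal, the expected number of missed events would be 1 × .01 = .01 to 4 × .01 = .04. A reader might infer that the primary result is biased towards the device by a known amount. The documents do not support that: they give neither the number of such subjects nor any evidence that their risk is higher.

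The point still merits correction because one event changes the conclusion (.9765 to .8368 with 215 prior subjects; .9875 to .8989 with 270), and because with the 215-subject prior even one unfollowed subject can tip the result, depending on how 18.5 is read.

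**What to change.** Reconcile 7.8, 7.11 and 10.2 with the enrollment point and follow-up duty that 7.10 already states and 14.3.1 shares.

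- **7.8:** define a screen failure as a consented subject who was not enrolled, that is, to whom no local anesthetic was delivered. Delete 'or during', and tie the remaining wording to enrollment. Section 8.1 times the procedure from Tip contact with bone, so a rule that ends at the procedure would still catch subjects who have had the anesthetic.
- **10.2:** replace 'prior to treatment' with 'prior to enrollment' for the screen-failure label.
- **7.11:** state that treated status does not decide screen-failure status or follow-up.
- **7.10 or 8.1:** state that an enrolled subject whose measurement is stopped keeps the 7.10 follow-up contacts unless consent for follow-up is itself withdrawn, and record the two decisions separately.

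The 8.1 instruction on stopping device use is untouched. The cost is a short amendment with IRB and FDA review, and no visits beyond those 7.10 already requires.

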7.9 SUBJECT IDENTIFICATION

Subjects who consent to participate shall be assigned a unique Subject Identification Number to de-identify their information. This Subject Identification Number will be captured on the Screening & Enrollment Log and used to identify them on all source documents and eCRFs thereafter.

7.10 SUBJECT ENROLLMENT

The point of enrollment occurs when the Investigator delivers the local anesthetic. All enrolled subjects, including those found to be ineligible after consent, will be followed for the next 30 days in accordance with the Schedule of Assessments.

7.11 TREATED SUBJECTS

A treated subject is an enrolled subject who has had the OsteoProbe measurement procedure completed and a BMSi measurement was recorded. All treated subjects, including those found to be ineligible after enrollment, will be followed for the next 30 days in accordance with the Schedule of Assessments.

8. STUDY VISIT PROCEDURES

8.1 VISIT 1: SCREENING/PROCEDURE VISIT

Note: The Screening/Procedure visit may take place over multiple days, but the OsteoProbe procedure must be completed within 7 days of signing the ICF.

Upon successful documentation of informed consent, the subject will be screened to confirm subject eligibility. The screening will include a documentation of demographics, medical history, physical exam with vitals (temperature, blood pressure, pulse and respiratory rate), x-rays to rule out tibial fractures or implants, pregnancy evaluation (for women of childbearing potential only), work status, and concomitant medications.

Upon successful confirmation of subject eligibility, the subject will undergo the following:

Baseline NRS Survey

- The subject will complete a baseline Numerical Rating Scale (NRS) Survey right before initiating the OsteoProbe test procedure

OsteoProbe Test Procedure

- The Investigator will clean the test site and apply a local anesthetic agent prior to performing the OsteoProbe procedure, as outlined in the Procedure Guide, with the assigned device. The Investigator will note the anesthetic agent used, time of delivery and the volume administered in the subject's study records.
- The procedure start time will be recorded as the time of first insertion of the Tip to the bone surface
- The procedure stop time will be recorded as the time the Tip is removed from the skin following the final indentation
- The Investigator will consider the procedure to be successful once the OsteoProbe software displays the BMSi
- If the Investigator cannot complete the procedure for any reason, they should stop the use of the device on this subject and treat the subject per SOC

Post-Procedure (< 60 Minutes)

- The Investigator or delegate will apply a dressing to the test site per SOC
- The Investigator or delegate will record the BMSi Score
- The subject will complete the post-procedure Numerical Rating Scale (NRS) Survey—*this pain survey must be administered prior to performing any adverse event or device deficiency evaluations to prevent information from these assessments biasing the subject's responses.*
- The Investigator or delegate will record adverse events and device deficiencies, if applicable
- The Investigator or delegate will review the suggested post-procedure regimen with the subject per the User Manual
- The Investigator or delegate will perform a review of concomitant medications with the subject

8.2 VISIT 2: 1-DAY FOLLOW-UP (+2 DAYS)

To allow the Investigator's assessment of the subject's progress, the subject will be contacted by the Investigator for a telehealth appointment and interviewed/examined to assess the following:

- The subject's Numerical Rating Scale (NRS) pain score –*this pain survey must be administered prior to performing the other visit assessments to prevent information from these assessments biasing the subject's responses.*
- New or updated adverse events, if applicable
- Current work status
- Review of concomitant medications
- Current body temperature (for telehealth visits, the patient will take their temperature during the visit while being observed and display thermometer reading for the Investigator to confirm and record)

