1.1 SCHEDULE OF EVENTS

Activity	Visit 1 Screening/ Procedure ¹	Visit 2 1-Day ^{2,3} (+ 2 days)	Visit 3 7-Day ^{2,3} (±3 days)	Visit 4 30-Day ² (±10 days)	Unscheduled
Informed Consent	X	-	-	-	-
Inclusion/Exclusion Criteria Review	X	-	-	-	-
Demographics	X	-	-	-	-
Medical History	X	-	-	-	-
Physical Examination (including vitals)	X	-	-	-	-
X-Rays (AP & Lateral)	X	-	-	-	-
Pregnancy Evaluation/Test ⁴	X	-	-	-	-
OsteoProbe Test Procedure	X	-	-	-	-
NRS Pain Score	X ⁵	X	X	X	X
Record BMSi Score	X	-	-	-	-
Body Temperature		X	X	X	X
Record/Review Concomitant Medications	X	X	X	X	X
Record/Review Adverse Events	X ⁶	X ⁶	X ⁶	X ⁶	X ⁶
Record/Review Device Deficiencies	X	-	-	-	-
Work status	X	X	X	X	X

¹ The Screening/Procedure visit may take place over multiple days, but the OsteoProbe procedure must be completed within 7 days of signing the ICF.

² To be conducted as telehealth visits with video interviews; option of in-person visits is acceptable if that is preferred by a subject or the Investigator.

³ Measured from the date of the OsteoProbe procedure.

⁴ Female subjects of child-bearing potential only. Negative pregnancy status can be based on self-reported sexual history and contraception use. An in-clinic test must be performed using urine dipstick when the subject thinks there is a potential that they might be pregnant.

⁵ The NRS Survey must be completed once prior to the OsteoProbe procedure (baseline) and again following completion of the procedure.

⁶ X-rays will be ordered by the Investigator to evaluate any adverse event that may be related to a potential tibial fracture based on clinical exam and/or adverse event details provided by the subject.

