6.5 TREATMENT/CONTROL GROUPS AND BLINDING

A total of forty (40) subjects will be enrolled in a single-arm investigational “OsteoProbe” group. In this investigation, neither the Investigator nor the subject can be blinded to the investigation group assignment after undergoing the measurement with the investigational device.

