8.6 UNSCHEDULED VISITS

Subjects may be evaluated at unscheduled post-procedure visits by the Investigator or delegated staff as needed. During unscheduled in person or remote visits with the Investigator or delegated staff, the Investigator or delegate will assess the subject's progress and perform/record the following:

- Numerical Rating Scale (NRS) pain score – *this pain survey must be administered prior to performing the other visit assessments to prevent information from these assessments biasing the subject's responses.*

- New or updated adverse events, if applicable. Adverse events must be reviewed and assessed by the Investigator.
- Current work status
- Review of concomitant medications
- Current body temperature (for telehealth visits, the patient will take their temperature during the visit while being observed and display thermometer reading for the Investigator to confirm and record)

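### Sections 8.2-8.4 leave the follow-up pain rating with the Investigator, who under 8.1 also performs the measurement, so the operator may collect ratings of pain from the operator's own procedure

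*Combined protocol and SAP*

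**What the plan says.** - **Procedure (8.1).** "The Investigator will clean the test site and apply a local anesthetic agent prior to performing the OsteoProbe procedure". No delegate is named for this step. Afterwards, "The subject will complete the post-procedure Numerical Rating Scale (NRS) Survey"; the section does not say who hands the survey over. The other post-procedure tasks are given to the Investigator or a delegate.
- **Scheduled follow-up (8.2, 8.3, 8.4).** Each section says that "the subject will be contacted by the Investigator for a telehealth appointment and interviewed/examined to assess the following", with the NRS first in the list and no delegate mentioned. A footnote to the Schedule of Events (1.1) describes the mode: "To be conducted as telehealth visits with video interviews; option of in-person visits is acceptable if that is preferred by a subject or the Investigator".
- **Safeguard for the NRS (8.2, repeated in 8.3, 8.4 and 8.6).** "this pain survey must be administered prior to performing the other visit assessments to prevent information from these assessments biasing the subject's responses".
- **Unscheduled visits (8.6).** Here a delegate is named: "the Investigator or delegate will assess the subject's progress and perform/record the following". The NRS is on that list. Adverse events must still be assessed by the Investigator.
- **Setting.** There are forty subjects at one site (7.2), recruited from the Investigators' usual patients (7.1), with no control group (6.2). On blinding, 6.5 states that "neither the Investigator nor the subject can be blinded to the investigation group assignment after undergoing the measurement with the investigational device".
- **Role of the endpoint.** Pain from the procedure is named in the secondary objective (5.2), and the NRS is the first secondary endpoint (6.4). Section 18.6 plans descriptive statistics only. It lists the NRS at procedure, Day 1 and Day 7 and omits the Day 30 score that 6.4 includes. That is a separate inconsistency to reconcile.

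**The concern.** A 0-10 pain rating is subjective, and a patient may give a kinder answer to the clinician who performed the procedure than on a form or to someone else. The wording of 8.2-8.4 steers towards that situation without requiring it. The protocol already accepts that the NRS needs protecting from bias, because it fixes when the survey is given. It also accepts that Investigator bias deserves a remedy, because an independent committee adjudicates adverse events and deviations (14.5). Neither measure covers who collects the pain score.

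At stake is how far the follow-up pain summaries can be trusted. Lower scores favor the device, 4.4 justifies the study partly by a design meant to measure without pain, and the data are intended for a de novo submission (20.4). With no control arm, a reporting bias has nothing to cancel against.

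**Working it through.** The plan states no figure for NRS pain, so the check is mainly a comparison of sections.

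**1. Who is named for each step**

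| Step | Section | Person named | Delegate named? |
|---|---|---|---|
| Anesthetic and measurement | 8.1 | Investigator | No |
| Baseline and post-procedure NRS | 8.1 | Subject completes; no administrator named | Not stated |
| Other post-procedure tasks | 8.1 | Investigator or delegate | Yes |
| Day 1, 7, 30 visits, NRS first | 8.2-8.4 | Investigator | No |
| Unscheduled visits, NRS first | 8.6 | Investigator or delegate | Yes |

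The scheduled visits, which supply the endpoint data, have narrower wording than the unscheduled ones. Since 8.6 already lets a delegate take an NRS score, the protocol shows no objection in principle to someone else collecting it.

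**2. Is it the same individual?** There is one site and one Principal Investigator (section 1). However, 20.2 refers to Sub-Investigators, so a different physician could make the follow-up call. The text permits the same person and does not require it.

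**3. Do the existing safeguards cover this?** The NRS-first rule stops other visit questions from coloring the answer; it says nothing about the person asking. The committee in 14.5 reviews adverse events and deviations, not NRS scores. Neither covers it.

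**4. What is exposed?** Only the follow-up NRS summaries. The plan's one sizing figure reproduces without any NRS input. The inputs are a Jeffreys prior, 215 prior subjects with 0 events, and 40 trial subjects with 0 events (18.2):

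- Posterior: Beta(0.5 + 0, 0.5 + 215 + 40) = Beta(0.5, 255.5).
- P(rate < 0.01) = 0.9765, matching the stated .9765.

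Pain scores do not enter that calculation, so the primary conclusion cannot move on this account.

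**5. What limits the size?** The NRS cannot go below 0 (section 9). If the true mean at a visit is m, the mean under-report cannot exceed m: at most 0.5 point when m = 0.5, and at most 0.25 point when m = 0.25. Exclusion 14 in 7.4 removes people whose pain conditions, chronic or intermittent leg pain among them, are judged to preclude evaluation, so background pain should be low. If procedural pain fades over the month (an assumption, since the documents give no time course), there is most room for under-reporting at Day 1 and least at Day 30.

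**The case against.** The strongest reply is that the Investigator is a role, that one bias safeguard is already in place, and that nothing is tested on the NRS. All three are true, and they keep this a minor point. They do not answer it, because the text neither separates the operator from the collector nor says how the follow-up score is taken.

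A reader might infer more than the documents support:

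- **That the operator does collect the score.** This is an inference from one role name at one site. The supportable wording is that the operator may.
- **That the mode switches from self-completion to interview.** 8.1 has the subject complete the survey, but 8.1-8.4 and 8.6 all call it a survey that is administered, and exclusion 12 in 7.4 assumes subjects complete the NRS surveys generally. The interview wording introduces the whole visit list. The follow-up mode is unsettled, not shown to differ.
- **That change from baseline is confounded.** Section 18.6 specifies no change-from-baseline analysis.
- **That the NRS is the only evidence on pain.** Pain and discomfort are listed risks (4.1), adverse events are collected at every visit and adjudicated (14.5), and pain medication is recorded (13). These would probably show material pain, although they are gathered at the same Investigator visits.
- **That the bias can be expressed in standard errors.** Assuming an SD of 2 gives SE = 2/√40 = 0.316, and an assumed shift of 0.5 to 1.0 point would then be 1.6 to 3.2 SE. Neither input is in the documents. With an SD from 1 to 2.5, the 0.5-point shift alone runs from 3.2 down to 1.3 SE. The calculation also ignores the floor and applies one shift to all three visits.

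It is also fair to say that a form shown to the operator on camera would keep part of the problem, and that home-completed forms need handling.

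**Conclusion.** The point holds as a cheap improvement. As written, 8.2-8.4 allow the operator to collect the Day 1, 7 and 30 pain ratings, and no stated safeguard addresses that. The follow-up NRS summaries are therefore open to under-reporting. The downward direction is a plausible inference about how patients answer their own clinician, not something the documents show. The size cannot be derived from the plan; the floor at 0 probably limits it, and it matters most at Day 1. No hypothesis test, threshold or success criterion depends on the NRS, and the primary device-related SAE analysis is unaffected. The conclusion rests on reading the Investigator in 8.1 and in 8.2-8.4 as possibly the same person, which the protocol leaves open.

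**What to change.** In 8.2, 8.3 and 8.4, add one sentence giving either of two routes:

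- the subject completes the same NRS survey unaided before the Investigator's interview begins; or
- an existing delegate who did not perform the measurement administers it.

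Add CRF fields for who collected the score, whether that person performed the measurement, and the mode (self-completed or verbal). The rest of the visit, including adverse event assessment, stays with the Investigator. If the self-completed form has to be confirmed on video, having the delegate do this avoids showing the rating to the operator.

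**Cost.** No new staff or visits. There is some coordination at three visits, and forms completed at home need a source-document rule. Section 15 expects the paper CRFs in the site binder to be the source but allows supplemental source, so these forms can be retrieved and filed there. An occasional form will be forgotten and the score taken verbally, which the mode field would show. If the sponsor regards the change as affecting data validity, 19.3 requires an amendment submitted to the IRB and FDA.
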